#### Overview

[figure not shown]
Previous observational studies demonstrate aspects of the conceptual model (Figure 1), but no intervention studies have examined these relationships. The *objective* of this aim is to understand longitudinal relationships between symptoms, depression, and quality of life. *We are not powered to examine direct intervention effects*

on quality of life, but, as supported by a vast literature on mediation analysis, we are adequately powered to examine mediational pathways by which the intervention influences quality of life (see "power analysis" below). We will test the hypothesis that symptom experience, measured as symptom severity using the ESAS total score, and the number of depressive symptoms, measured by the PHQ-9 score, mediate the relationship between the intervention and health-related quality of life, measured by the KCCQ quality of life subscale. This hypothesis will be tested using a structural equation modeling framework because the variables are measured longitudinally, and we are interested in testing mediation pathways and using multiple dependent variables. The rationale for this aim is that a fundamental understanding of the relationships between symptoms, depression, and quality of life is critical to the further refinement of therapeutic strategies to improve symptoms and quality of life. For example, we will understand the relative importance of each path of intervention effect, and consider strengthening or diminishing the palliative symptom management or psychosocial care components. If the intervention is not successful, a deeper understanding of the relationships between these variables will guide the content of future interventions to improve symptoms and quality of life. Furthermore, examining these variables in a longitudinal study will provide much stronger evidence for their relationships.

Data Analysis Plan

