The analyses for this aim will be carried out using Mplus following well-established statistical methods for testing the mediated effect with longitudinal data and multiple mediators. The general structure of the proposed model is depicted in Figure 3. This model is a simplified version of the overall conceptual model (Figure 1). The model will be estimated in a parallel process growth modeling framework where the change in symptom severity over time will be estimated simultaneously with the change in the number of depression

Figure 3. Structure of the mediational model

symptoms over time, each of which will be captured by latent initial status and slope factors. The a1 path from the intervention to symptom severity will measure the impact of the intervention on changes in symptom severity (the symptom severity slope factor) and the a2 path will test the impact of the intervention on changes in the number of depression symptoms (the depression slope factor). The b1 path from depression to symptom severity is included to test the hypothesis that some of the impact of depression on quality of life will occur through reduced symptom severity. The b2 and b3 paths capture the effects of the symptom severity and depression slope factors on health-related quality of life measured at the end of the study. The overall fit of the proposed model, the significance of the individual paths, and the significance of the mediated effects will be assessed. The mediated effects will be calculated using the product of coefficients method and will be evaluated for statistical significance by a bias-corrected bootstrapped standard error estimate. Three specific indirect effects will be estimated: (1) the indirect effect of the intervention on health-related quality of life through symptom severity (a1\*b2), (2) the indirect effect on quality of life through depression (a2\*b3), and (3) the indirect effect on health-related quality of life in a multiple mediator framework through the intervention's impact on depression and the impact of depression on symptom severity (a2\*b1\*b2).

Through exploratory analyses, we will examine the same model using our alternative measures of the symptom experience (symptom distress, GSDS) and health-related quality of life (QUAL-E subscales).

Aim 2 Power Analysis

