Power calculations were based on the magnitude of the individual paths, as well as the power to test each of the three proposed specific indirect effects. Power was calculated in Mplus using a Monte Carlo simulation.

 The population model followed the structure of Figure 3, but was estimated as a parallel process growth model. For consistency with the power estimates under Aim 1, moderate-sized effects from the intervention to symptom severity and depression were specified (i.e., 13% of the variance in symptom severity and depression accounted for by the intervention). Based on an earlier cross-sectional study showing large correlations (>.50) between symptoms, depression, and quality of life, large effects (26% of the variance in outcomes) were specified for the paths from depression to symptom severity, from depression to health-related quality of life, and from symptom severity to quality of life. Assuming a two-sided  $\alpha = .05$ , power was sufficient ( $\geq .80$ ) to detect significant differences in each of the paths and in the three mediated effects. Power estimates may be considered conservative because Monte Carlo simulations do not calculate power using bootstrapped estimates, although this method has been shown to be the most powerful method for testing the significance of the mediated effect and will be used in this analysis.

**Aim 3. Examine the effect of the intervention on informal family caregivers' depression, burden, benefit-finding, social support, perceptions of patients' symptoms, quality of the patient-caregiver relationship, and contributions to patients' heart failure self-care.**

Similar to Aim 1, analyses of the repeated measures will be performed using maximum likelihood estimation (MLE) for incomplete data (SAS Proc Mixed) to examine the differences between caregivers of patients in the intervention compared to caregivers of patients in the control group over time on caregivers' depression, burden, benefit-finding, perceptions of patients' symptoms, quality of the caregiver-patient relationship, and contributions to patients' heart failure self-care.

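### Aim 2 reads path a1 as the intervention's impact on symptom change, but with a2 and b1 in the model a1 is only the part that does not pass through depression

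*Protocol*

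**What the plan says.** The Aim 2 Data Analysis Plan (Protocol) describes a parallel process growth model with slope factors for symptom severity and depression. It describes the two intervention paths in parallel terms: "The a1 path from the intervention to symptom severity will measure the impact of the intervention on changes in symptom severity", and "the a2 path will test the impact of the intervention on changes in the number of depression symptoms (the depression slope factor". A further path joins the mediators: "The b1 path from depression to symptom severity is included to test the hypothesis" that part of depression's influence on quality of life works through symptoms. Paths b2 and b3 lead from the two slopes to quality of life at the end of the study.

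The plan then says that "the significance of the individual paths, and the significance of the mediated effects will be assessed". "Three specific indirect effects will be estimated": a1 × b2, a2 × b3 and a2 × b1 × b2. Neither the total effect on the symptom slope nor the total indirect effect on quality of life is listed.

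The Aim 2 Overview gives the purpose: "we will understand the relative importance of each path of intervention effect", so that the symptom management or the psychosocial component can be strengthened or reduced. The Aim 2 Power Analysis assumes "13% of the variance in symptom severity and depression accounted for by the intervention" and 26% for the path from depression to symptom severity.

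**The concern.** Once the intervention is allowed to change depression, and depression to change symptoms, the coefficient on the remaining arrow from intervention to symptoms is a direct effect. It holds the depression slope fixed. The text nevertheless reads it as the intervention's whole impact on symptom change. In the model as described nothing comes between intervention and depression, so a2 is a total effect on its mediator while a1 is a residual one.

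The protocol expects the left-out part to be substantial: it assigns b1 a large effect, and its Background section says that depression intensifies other symptoms. Read as the plan reads it, a small or non-significant a1 could be taken in Aim 2 to mean little effect on symptoms when much of the benefit came by way of depression. Aim 2 also asks whether the intervention affects quality of life through symptoms and depression taken together, and no listed estimate answers that in one figure.

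**Working it through.** **Inputs.** 13% for each intervention path, 26% for b1 and two-sided α = .05 (Aim 2 Power Analysis); 312 patients, 15% deaths plus 10% dropout, 0.4 SD and 86% power (Sample Size, Aims 1-3); 1:1 allocation (Randomization).

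**The plan's own figure.** 312 × 0.75 = 234, or 117 per arm. Power for 0.4 SD is Φ(0.4 × √(117/2) − 1.96) = Φ(1.10) = 86.4%, which reproduces the stated 86%. The Aim 2 statement of at least .80 power cannot be reproduced exactly, because growth variances and slope reliability are not given.

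**Path algebra.** Let T be treatment, D the depression slope and S the symptom slope, all standardised.

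- D = a2 × T + error
- S = a1 × T + b1 × D + error
- Substituting: S = (a1 + a2 × b1) × T + error

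The total effect is therefore a1 + a2 × b1. With the protocol's shares, a2 = √.13 = .361, b1 = √.26 = .510 and a2 × b1 = .184.

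- If 13% is the *direct* share: a1 = .361 and the total is .361 + .184 = .544. Then a1 is 66% of the total, and the intervention's total share of symptom-slope variance is .544² = 30%.
- If 13% is the *total* share: the total is .361 and a1 = .361 − .184 = .177. Then a1 is 49% of the total.

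**How often a1 reaches significance.** Simulation with 4,000 trials per setting, N = 234, two-sided .05 and slopes observed without error. The total effect is tested by regressing S on T, and a1 by regressing S on T and D. An effect of 0.4 SD corresponds to a standardised .4/√(.16 + 4) = .196.

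| Setting | a1 | total | a1 significant | total significant |
|---|---|---|---|---|
| 13% read as direct share, b1 = .51 | .361 | .544 | 100% | 100% |
| 13% read as total share, b1 = .51 | .177 | .361 | 88% | 100% |
| 0.4 SD total on both mediators, b1 = .51 | .096 | .196 | 40% | 86% |
| same, b1 = .3 (assumed) | .137 | .196 | 60% | 86% |
| same, b1 = .7 (assumed) | .059 | .196 | 24% | 86% |
| 0.4 SD read as direct a1, b1 = .51 | .196 | .296 | 95% | 99.7% |
| all benefit through depression, a2 = .361, b1 = .51 | 0 | .184 | 5% | 81% |

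In the third row, 54% of the trials with a significant total effect have a non-significant a1. With an assumed slope reliability of 0.6, that row becomes 40% against 65%.

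**Why the planning effect matters.** 13% of variance corresponds to 2 × √(.13/.87) = 0.77 SD, whereas 0.4 SD corresponds to .16/4.16 = 3.8%. The Aim 2 inputs are said to be consistent with Aim 1, but they are much larger. The size of the problem depends on which of the two is nearer the truth.

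**The case against.** A reader might infer that a real symptom benefit will often be reported as absent. The documents do not support that.

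- At the planning values of the Aim 2 Power Analysis, a1 is missed in 0% to 12% of trials, in line with the stated power of at least .80. Frequent misses need a smaller effect, such as 0.4 SD in total, or a benefit that runs mostly through depression.
- The trial does not depend on a1 to show a symptom benefit. Symptom distress is a pre-specified Aim 1 secondary endpoint, analysed by intent to treat in a mixed model for which no depression term is stated. That gives the total effect of arm. The relief is partial: Aim 1 names symptom distress, while the Aim 2 mediator is symptom severity by the ESAS total score, and Aim 1 does not separate routes.
- The route through depression to symptoms is estimated, as a2 × b1 × b2.
- Nothing says that a non-significant a1 means no benefit. Item 8 of Limitations and Considerations looks at the magnitude of paths as well as their significance.

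Two further inferences also fail. The three specific indirect effects are not misdefined: each carries its formula, and leaving the serial path out of the first two is normal usage. Nor is the 13% shown to be wrong: it can be read as a direct or a total share, and either reading is coherent.

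It can also be said that sums of listed terms belong in an analysis plan that is not shown. That is fair for the sums alone. It does not cover the sentence on a1, which gives a wrong interpretation. For comparing components the direct effect may well be a relevant quantity, but it must be named as such.

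**Conclusion.** The point holds as an error of interpretation in the protocol text. Path a1 is the direct effect on symptom change, not the impact on it, and it is not on the same footing as a2. With the protocol's values it is about half or two thirds of the total effect, depending on what the 13% means. In Aim 2 it can understate the symptom effect, and it can miss it when much of the benefit runs through depression.

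The path algebra needs only the model as described in the text (Figure 3 is not shown) and the direction of b1 as the plan assumes it. The shares also take a1 and a2 × b1 to have the same sign. The significance rates rest further on error-free slopes and, for the 0.4 SD and full-mediation rows, on assumed effects. The consequence is confined to how Aim 2 is read. It deserves correction because the Aim 2 Overview means to use these paths to judge the intervention's components.

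**What to change.** 1. In the Aim 2 Data Analysis Plan, describe a1 as the direct effect on the symptom slope that does not pass through the depression slope.
2. Add two derived parameters, with the bootstrap already planned: the total effect on the symptom slope, a1 + a2 × b1, and the total indirect effect on quality of life, a1 × b2 + a2 × b3 + a2 × b1 × b2. Base statements about impact on symptoms on the first and statements about overall mediation on the second.
3. Keep the three specific indirect effects for comparing routes. If a1 × b2 + a2 × b1 × b2 and a2 × b3 + a2 × b1 × b2 are also shown, state that both contain a2 × b1 × b2, and do not rank components on them.
4. In the Aim 2 Power Analysis, say whether 13% is the direct or the total share for symptom severity.

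The cost is a few lines of Mplus code and some changed wording. No new data are needed.

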#### Data Analysis for Aims 4-6

The qualitative data collection and analysis is designed to be flexible and iterative in nature. Using the Consolidated Framework for Implementation Science (CFIR), we will analyze project data to address each specific aim, then conduct a final, more comprehensive analysis to examine differences and similarities of CFIR and other implementation influences that emerge within the current implementation context (Denver Metro Area health care systems) compared to the planned implementation contexts (rural health systems). This approach is informed by the CFIR, which reinforces the importance of understanding implementation barriers and facilitators within the context that an intervention or innovation is planned, implemented, and sustained. By focusing our analysis within each implementation context – current and planned –we are able to describe and disentangle the importance of these different contexts and their influence on perceived facilitators and barriers of CASA implementation and scale-up.

Aim 4. Identify valuable core CASA intervention content and processes from the perspectives of patients and intervention team members.

Using a combination of inductive and deductive methods, we will create an evolving set of codes linked to units of text (fragments, sentences or paragraphs) using the Atlas.ti software package. [name] and the research assistant will serve as primary coders for qualitative data, and [name] will review coding and codebooks as they are developed. We will follow a systematic process to enhance coder agreement in assigning codes and a peer debriefing process that requires regular meetings with [name], and the research assistant to review and refine codes, code definitions and conceptual boundaries for our analysis. The iterative analysis will begin by using the a-priori codes based on intervention content and structures and questions used for data collection, with continual refinement of codes and adding new codes as new insights emerge. Through systematic coding we will quickly develop working themes and hypotheses that will be examined (and inform any minor changes in data collection interview/survey guides). We will both audiotape and take detailed notes during all data analysis meetings in order to document proposed codes and code revisions, proposed themes and their descriptions, and other decisions made during these working meetings.

Protocol: Improving Symptoms and Quality of Life in Chronic Heart Failure

PI: [name],

COMIRB #: 11-0969

Aim 5 Identify barriers and facilitators of CASA implementation and sustainability from the perspectives of providers whose patients have received the CASA intervention and intervention team members (interpretive-focused formative evaluation), and

Aim 6: Determine interest and capacity of providers in rural settings to adopt CASA's team-based model of outpatient palliative and psychosocial care (developmental formative evaluation)

Although we will primarily analyze qualitative data for Aim 5 and Aim 6 separately, our data collection methods and analytic approaches are designed so we can apply an overlapping set of CFIR constructs as a-priori codes for addressing both study aims. Using overlapping CFIR codes will both allow us to develop contextually grounded understandings of CASA implementation and sustainability and explore important similarities and differences within and across settings. For the proposed evaluation, our analysis will focus on those selected CFIR constructs related to provider and organizational influences on CASA implementation and sustainability, including factors related to organizational context itself. Specifically, we will use codes reflecting the CFIR domain of "Inner Setting" to help us understand organizational context with which CASA is or will be implemented, and a-priori codes for the "Outer Setting," which will help us understand more about, for example, different patient and resource needs and health system expectations and pressures that influence implementing a team-based palliative care intervention like CASA in urban and rural environments. For the analysis of rural interviews, we are particularly interested in understanding the Inner Setting construct of Readiness for Implementation. Understanding this construct will help us describe organizational capacity, resources, and infrastructure that will influence decisions about CASA implementation and sustainability.

Using a combination of inductive and deductive methods, we will create an evolving set of codes linked to units of text (fragments, sentences or paragraphs). This iterative analysis will begin by using the a-priori CFIR constructs as codes, with continual refinement of codes and adding new codes as new insights emerge. Through systematic coding and rating of constructs as either a positive (facilitator) or negative (barrier) influence, we will quickly develop working themes that will be examined within each aim. We will both audiotape and take detailed notes during all data analysis meetings in order to document proposed codes and code revisions, proposed themes and their descriptions, and other decisions made during these detailed working meetings. We will use several recommended strategies to enhance the validity or credibility of qualitative findings: (1) structured interview guides administered by well-trained interviewers, (2) coding templates and detailed descriptions of codes, coding decisions and analysis strategies to document all phases of the data analysis (audit trail); and (3) team approaches (at least two analysts) to develop coding templates and independently code subsets of transcripts/notes to determine their agreement and application of codes and code definitions.

### Sample Size

#### Aims 1-3

We plan to accrue 312 patients and anticipate 15% of the participants will die due to progression of their HF and an additional 10% will dropout due to miscellaneous reasons. Thus, approximately 117 participants per arm will have all four assessments. With this sample size, we have 86% power to detect a moderate effect of 0.4 SD (two-sided test,  $\alpha=0.05$ ). This corresponds to a change in KCCQ score of 6-8, depending on the standard deviation in our sample (prior standard deviations of the KCCQ overall score range from 15-20). A change in KCCQ score of 6-8 is above the clinically meaningful change in KCCQ score.

#### Aims 4-6

The sample sizes are described in Table 9.

### Limitations and Considerations

1. *Given the multi-faceted intervention, it will be unclear which components are essential.* The intervention was specifically designed to have multiple components because symptoms and quality of life are complex phenomena. Multicomponent care interventions need to be tested as a whole. The quality improvement literature is rife with evidence that unimodal interventions have a low likelihood of success and interventions that have been shown to be effective in some studies usually have modest effects unless they are combined. The analyses in Aim 2 will contribute to understanding the relative importance of intervention components.
2. *If the intervention is not successful in showing improvements in any of the outcome measures, this will be an important, if undesired result, but study will still contribute to the evidence base regarding models of palliative care delivery and specifically HF palliative care.* The process monitoring will inform future interventions.
3. *What is the potential for contamination?* It is possible that a provider may have patients in both the intervention and control arms. However, this is unlikely to have a significant effect because: a) these patients will represent a very small percentage of the patient panels of a given provider; b) providers will not know whether care recommended for a given intervention patient would be appropriate for a given control patient; and c) there is no clear evidence that specific recommendations for a given patient by a specialist or collaborative team are carried over to other patients by providers; and d) changing provider behavior is notoriously difficult. If any contamination did take place, it would bias results toward the null and would not invalidate any differences detected in outcomes.
4. *Recruitment problems.* The recruitment goals are modest and reasonable for each site. If necessary, resources can be diverted to increase efforts at one of the recruitment sites. We can also add recruitment of outpatients using the same enrollment criteria and conduct a sensitivity analysis to evaluate if outcomes are different for those recruited in this setting.
5. *Informal caregiver outcomes are not measured.* This is a patient-focused intervention; caregiver issues are not the primary focus. Prior work has shown the importance of caregivers in HF care, and caregiver involvement is part of quality palliative care. However, caregiver outcomes are beyond the scope of this study.
6. *Key palliative care elements, such as spiritual care, are not explicitly mentioned.* The palliative care specialist is on the team to bring all aspects of palliative care to patient care. If spiritual distress is identified, for example, the team can enlist a chaplain's assistance. The role of spiritual well-being in quality of life will be examined in Aim 3 and the intervention can be modified to formally include spiritual care if necessary.
7. Even if the intervention is not successful, we will still be able to conduct analyses examining the proposed relationships among depression, symptoms, and quality of life, and these analyses will inform the focus of future interventions designed to improve quality of life. In fact, if intervention and control patients are combined in the analysis, we will have adequate power to include functional status in the model in order to make inferences about relationships between symptom distress/severity, depression, and functional status.
8. If the correlations assumed in the power calculation are too high and the analysis is underpowered, the model will still be useful for examining the hypothesized relationships among variables. We would still examine the magnitude and significance of the individual paths, but perhaps not expect that the indirect effects will be significant.

Protocol: Improving Symptoms and Quality of Life in Chronic Heart Failure

PI: [name],

COMIRB #: 11-0969

